#### 4.2.4 Site and Researcher Information

Data of the study sites and of the Researcher will be presented in summary tables.

The summary tables for site information will show absolute and relative frequencies for the institution type (private practice/ private hospital, general hospital, academic/ university hospital, other), the type of unit (general population, transplant, drug user, HIV/ HCV co-infection, hepatocellular carcinoma [HCC]), and the site location (urban, rural). Regarding type of unit multiple answers per site are possible.

The principle researcher experience will be summarized by presenting for each therapeutic specialty (hepatology, infectious disease, gastroenterology, internal medicine, transplant, general practitioner) the number and percentage of principle researchers, who have the specific experience. Furthermore, the number and percentage of sites with at least one researcher (i.e. including co-researcher) of the therapeutic specialty concerned and the number of HCV-infected patients typically seen per month at the site (<25, 25-50, 51-75, 76-100, >100), including the patients seen by co-researcher, will be summarized. Note: Multiple therapeutic specialties could be reported per researcher.

An overview of Tables for site and researcher information is given in Table 6.

**Table 5 Overview of Outputs for Site and Researcher Information**

Output Title	Output Name	Short Name	Analysis Population
Site Information - <country>	tsi_<c>		Sites with patients
Researcher Experience- <country>	tre_<c>		Sites with patients

The layouts of the tables mentioned above are provided in Part II of the SAP (Table Shells).

#### 4.2.5 Patient Disposition

The frequencies of patients belonging to the different populations (i.e. EP, TP, CP, CPSFU; SP) will be summarized by genotype and cirrhosis status and overall using the EP analysis groups as specified in section 4.2.1. The reasons for exclusion from a particular population will be also summarized in the frequency tables. Additionally, information on patient disposition will be listed.

Furthermore the frequency of patients not completing the study as defined per protocol (i.e. no HCV RNA assessment performed at least 10 weeks post-treatment), will be summarized by treatment regimen and cirrhosis status and additionally by genotype and cirrhosis status and overall for the SP and CP. The reasons for not completing the study as entered on the CRF will be displayed (i.e. failure to return, insufficient virological response (HCV RNA detectable at end of treatment, relapse post-treatment), patient never started treatment, withdrawn consent, death, other).

Additionally, the main reason for early termination of the ABBVIE regimen (AE or SAE [Physician decision], virological non-response [Physician decision], rebound or breakthrough [Physician decision], resistance to DAA [Physician decision], patient refused to continue treatment, patient withdrew consent to participate in the study, lost to follow-up, other, unknown [if actual duration is shortened for more than 7 days]) and Ribavirin (Anemia, Nausea/Vomiting, Rash, Other) will be summarized by treatment regimen and cirrhosis status and additionally by genotype and cirrhosis status and overall for the following different analysis populations: CP and SP.

Finally the study regimens assigned at baseline will be summarized (a) by genotype and cirrhosis status and (b) by genotype and pre-treatment status (treatment naïve vs treatment experienced) for CP and SP.

An overview of tables is given in Table 7.

**Table 6 Overview of Outputs for Patient Disposition**

Output Title	Output Short Name	Analysis Population
Patient Disposition by Genotype and Cirrhosis Status – EP - <country>	tdis_<c>_gc_ep	Patients Enrolled
Listing of Patient Disposition - EP- <country>	ldis_<c>_ep	Patients Enrolled
Premature Termination of the Study and its Main Reason by <Treatment Regimen/ Genotype> and Cirrhosis Status - CP - <country>	tps_<c>_<t/g>c_cp	Core population
Premature Termination of the Study and its Main Reason by <Treatment Regimen/ Genotype> and Cirrhosis Status - SP - <country>	tps_<c>_<t/g>c_sp	Safety population
Premature Termination of Treatment and its Main Reason by <Treatment Regimen/ Genotype> and Cirrhosis Status - CP - <country>	tpt_<c>_<t/g>c_cp	Core population
Premature Termination of Treatment and its Main Reason by <Treatment Regimen/ Genotype> and Cirrhosis Status - SP- <country>	tpt_<c>_<t/g>c_sp	Safety population
Treatment Regimen by Genotype and Cirrhosis Status - CP - <country>	ttr_<c>_gc_cp	Core population
Treatment Regimen by Genotype and Cirrhosis Status - SP - <country>	ttr_<c>_gc_sp	Safety population
Treatment Regimen by Genotype and Pretreatment Status - CP - <country>	ttr_<c>_gpe_cp	Core population
Treatment Regimen by Genotype and Pretreatment Status - SP - <country>	ttr_<c>_gpe_sp	Safety population

The layouts of the tables mentioned above are provided in Part II of the SAP (Table Shells).

#### 4.2.6 Baseline Characteristics

All baseline and disease characteristics will be summarized for the CP stratified by genotype and cirrhosis status and overall, in accordance with the CP analysis groups specified in section 4.2.1). Corresponding baseline summaries will be repeated for the TP. In addition, these characteristics will be summarized by cirrhosis status and treatment regimen and overall for the SP, in accordance with the SP analysis groups specified in section 4.2.1. Summary statistics (n, mean, median, standard deviation [SD], minimum, maximum) will be generated for continuous variables (e.g. age and body mass index [BMI]). The number and percentage of patients will be presented for categorical variables (e.g. gender and race).

An overview of tables for baseline characteristics is given in Table 8.

##### 4.2.6.1 Socio-demographic characteristics

Demographic data will be summarized in a table displaying:

- Age (continuous and grouped by 18-65, 66-84, >=85 years)

- Gender (Male, Female)
- Race/ Ethnic Origin (White/Caucasian, Black, Asian/Oriental, Native American/American Indian, Other)
- Interleukin 28B (IL28B) genotype, rs12979860 (CC, CT, TT, Unknown)
- Interleukin 28B (IL28B) genotype, rs8099917 (TT, TG, GG, Unknown)
- Height [cm]
- Weight [kg]
- BMI [kg/m^2]

#### 4.2.6.2 CHC disease characteristics

CHC disease characteristics will be summarized in a table displaying:

- Years since diagnosis of HCV infection
- Mode of HCV Infection (Drug use (i.v.), Drug use (non i.v.), Sexual transmission, Occupational [HCV acquired while doing his/her job, e.g. physicians or nurses], Blood transfusion or transplantation, Perinatal, Contaminated medical device [other than i.v. drug use], Other, Unknown)
- Pretreatment Status (Naïve, Experienced)
- HCV Genotype and Subtype (as recorded in the CRF)
- Most recent stage of liver fibrosis (No cirrhosis, Transition to cirrhosis, Cirrhosis) [Only one method should be selected by the physicians to report stage of fibrosis. Nevertheless, if there are multiple answers the following priority will be used:
  1. Biopsy,
  2. Non-invasive,
  3. Clinical/best guess.

For biopsy as assessment method the respective categories are defined as follows:

- “No cirrhosis” is defined by “No fibrosis”, “Mild/minimal fibrosis”, “Moderate fibrosis”
- “Transition to cirrhosis” is defined by “Advanced Fibrosis”
- “Cirrhosis” is defined by “Cirrhosis”.]
- Assessment method for liver fibrosis staging (Biopsy, Non-invasive, Clinical/Best guess) [If multiple answers are ticked, the priority is as follows: biopsy, non-invasive, clinical/best guess.]
- Time between treatment start and biopsy assessment [months] (continuous)
- Time since biopsy [months] (categorized as ≤3, >3-6, >6-12, >12-24, >24-60, >60 months)
- Metavir fibrosis score (0, 1, 2, 3, 4)
- Ishak fibrosis score (0, 1, 2, 3, 4, 5, 6)
- Batts/Ludwig fibrosis score (0, 1, 2, 3, 4)
- Knodell fibrosis score (0, 1, 3, 4)
- Scheuer fibrosis score (0, 1, 2, 3, 4)
- Time between treatment start and FibroScan assessment [months] (continuous)
- Time since FibroScan [months] (categorized as ≤1, >1-2, >2-6, >6-12, >12-24, >24 months)
- FibroScan [kPa] (<8.8, 8.8-<9.6, 9.6-<14.6, ≥14.6)
- Time between treatment start and ARFI assessment [months] (continuous)
- Time since ARFI [months] (categorized as ≤1, >1-2, >2-6, >6-12, >12-24, >24 months)

- AFRI [m/s]
- Time between treatment start and FibroTest assessment [months] (continuous)
- Time since FibroTest [months] (categorized as ≤1, >1-2, >2-6, >6-12, >12-24, >24 months)
- Results of FibroTest (<=0.21, 0.22-0.27, 0.28-0.31, 0.32-0.48, 0.49-0.58, 0.59-0.72, 0.73-0.74, >=0.75)
- Esophageal varices (Yes, No, Unknown)
- History of liver decompensation (No - never decompensated, Yes - but currently compensated, Yes – still decompensated [including patients with a Child Pugh Score >=7], Current signs/symptoms – Total, Current signs/symptoms – Coagulopathy, Current signs/symptoms – Hyperbilirubinemia, Current signs/symptoms – Hepatic encephalopathy, Current signs/symptoms – Hypo-albuminemia, Current signs/symptoms – Ascites, Current signs/symptoms – Bleeding from esophageal varices [multiple answers are possible])
- Child Pugh Score (categorized as 5-6, 7-9, 10-15)

#### **4.2.6.3 CHC treatment history**

For treatment-experienced patients the most recent prior treatment and the outcome to prior treatment as reported by the investigator in the eCRF (Null response, Partial response, Breakthrough, Relapse, Sustained virological response (SVR) followed by reinfection, Discontinued [and none of the above], Unknown / None of the above) will be summarized in frequency tables. In addition to the frequency of each medication (IFN alpha, PEG IFN-alpha, IFN NOS, PEG IFN NOS, Ribavirin, DAA), the frequency of the combinations (pegIFN alpha + RBV, IFN alpha + RBV, XXX) will be summarized.

#### **4.2.6.4 Co-morbidities and co-infections**

A summary table will present the absolute and relative frequencies of HCV co-infections, CHC related comorbidities and other co-morbidities, in more detail:

- HCV Co-infections
  - Human immunodeficiency virus (HIV)
  - Hepatitis B virus (HBV)
  - Tuberculosis
  - Schistosomiasis
- Liver and/ or CHC related co-morbidities
  - Liver transplantation
  - Hepatocellular carcinoma
  - Steatosis (non-alcoholic)
  - Alcoholic liver disease
  - Primary biliary cirrhosis
  - Auto-immune hepatitis

- Wilson disease
- Cryoglobulinemia
- Porphyria cutanea tarda (PCT)
- Auto-immune skin disease
- Other co-morbidities
  - Kidney transplant
  - Chronic kidney disease (Mild, Moderate, Severe, Currently on dialysis, Currently not on dialysis)
  - Psychiatric disorders (Depression, Bipolar disorder, Schizophrenia, Personality disorder)
  - Diabetes mellitus (Type 1, Type 2)
  - Insulin resistance
  - Metabolic syndrome
  - Lipid disorder
  - Hyperthyroidism
  - Hypothyroidism
  - Cardiovascular disease (Myocardial infarction, Angina pectoris, Hypertension, Stroke)
  - Immunologically mediated disease
  - Hemophilia
  - Thalassemia
  - Sickle cell anemia
  - V. Willebrand disease
  - Psychoactive substance dependency (Active injection drug use, Inhalate cocaine, Marihuana/ cannabis, Opiate substitution)
  - Other

The patient's alcohol consumption will be displayed in a further table, i.e.:

- Alcohol use (None, Yes – occasional, Yes – regular, Ex-drinker [6 units/drinks per day, none in the last 3 months])
- Average number of units/drinks per week (if regular alcohol use is reported)

One unit/drink is defined as 10 milliliters (or approximately 8 grams) of pure alcohol and equals: 200 ml of beer or 100 ml of wine or 20 ml of hard liquor.

#### **4.2.6.5 CHC related and other laboratory data at baseline**

The laboratory data at baseline are the most recent available data prior to first administration of the ABBVIE REGIMEN (including day 1, see Table 5). All reported clinical laboratory test results will be assigned to one of the time points using the time windows specified in the Table 5.

A summary table will show CHC related laboratory data at baseline, i.e. HCV RNA in IU/mL, HCV RNA in log10 IU/mL, and HCV RNA categorized using 400,000, 800,000, 6,000,000 and 10,000,000 as cut-offs, ALT, ALT ratio, AST, AST ratio, APRI, FIB-4. ALT-ratio, AST ratio, APRI and FIB-4 will be calculated as follows:

ALT ratio = ALT value / upper limit of normal (ULN) of local laboratory

AST ratio = AST value / ULN of local laboratory

APRI =  $100 \times \text{AST [IU/L]} / (\text{ULN of AST [IU/L]} \times \text{Platelets [10}^{12}/\text{L]})$  (APRI= aspartate aminotransferase to platelet ratio index [1]; calculated, if laboratory assessments took place within 30 days)

FIB-4 =  $(\text{Age [years]} \times \text{AST [IU/L]}) / (\text{Platelets [10}^{12}/\text{L]} \times \text{Square root of ALT [IU/L]})$  (FIB-4= Fibrosis 4 index [2]; calculated, if laboratory assessments took place within 30 days )

In addition the following other key laboratory data at baseline will be summarized: γ-GT, total bilirubin, albumin, creatinine, creatinine clearance (continuous and categorize as Grade 1 [60-<LLN mL/min], Grade 2 [30-<60 mL/min], Grade 3 [15-<30 mL/min], Grade 4 [<15 mL/min]; if LLN is missing 75 mL/min is used), AFP, hemoglobin, platelets, prothrombin time, and INR (if documented instead of prothrombin time). The creatinine clearance will be calculated as follows:

Creatinine clearance [ml/min] =  $(140-\text{age}) \times \text{Weight (in kg)} \times \text{constant/Creatinine (in } \mu\text{mol/L)}$   
(constant is 1.23 for men and 1.04 for women; calculated by Cockcroft-Gault-Formula)

A further table CD4 and HIV-RNA test results are displayed for patients with HIV only.

**Table 7** Overview of Outputs for Baseline Characteristics

Output Title	Output Short Name	Analysis Population
Socio-demographic Characteristics by Genotype and Cirrhosis Status - CP - <country>	tdm_<c>_gc_cp	Core population
Socio-demographic Characteristics by Genotype and Cirrhosis Status - TP - <country>	tdm_<c>_gc_tp	Target population
Socio-demographic Characteristics by Treatment Regimen and Cirrhosis Status - SP - <country>	tdm_<c>_tc_sp	Safety population
CHC Disease Characteristics by Genotype and Cirrhosis Status - CP - <country>	tdc_<c>_gc_cp	Core population
CHC Disease Characteristics by Genotype and Cirrhosis Status - TP - <country>	tdc_<c>_gc_tp	Target population
CHC Disease Characteristics by Treatment Regimen and Cirrhosis Status - SP - <country>	tdc_<c>_tc_sp	Safety population
CHC Related Laboratory Variables at Baseline by Genotype and Cirrhosis Status - CP - <country>	tlcdb_<c>_gc_cp	Core population
CHC Related Laboratory Variables at Baseline by Genotype and Cirrhosis Status - TP - <country>	tlcdb_<c>_gc_tp	Target population
CHC Related Laboratory Variables at Baseline by Treatment Regimen and Cirrhosis Status - SP - <country>	tlcdb_<c>_tc_sp	Safety population
Other Key Laboratory Variables at Baseline by Genotype and Cirrhosis Status - CP - <country>	tkldb_<c>_gc_cp	Core population
Other Key Laboratory Variables at Baseline by Genotype and Cirrhosis Status - TP - <country>	tkldb_<c>_gc_tp	Target population
Other Key Laboratory Variables at Baseline by Treatment Regimen and Cirrhosis Status - SP - <country>	tkldb_<c>_tc_sp	Safety population
CHC Treatment History in Treatment Experienced Patients by Genotype and Cirrhosis Status - CP - <country>	tth_<c>_gc_cp_ep	Core population: treatment-experienced patients
CHC Treatment History in Treatment Experienced Patients by Genotype and Cirrhosis Status - TP - <country>	tth_<c>_gc_tp_ep	Target population: treatment-experienced patients
CHC Treatment History in Treatment Experienced Patients by Treatment Regimen and Cirrhosis Status - SP - <country>	tth_<c>_tc_sp_ep	Safety population: treatment-experienced patients
Co-morbidities and Co-infections by Genotype and Cirrhosis Status - CP - <country>	tcoi_<c>_gc_cp	Core population
Co-morbidities and Co-infections by Genotype and Cirrhosis Status - TP - <country>	tcoi_<c>_gc_tp	Target population
Co-morbidities and Co-infections by Treatment Regimen and Cirrhosis Status - SP - <country>	tcoi_<c>_tc_sp	Safety population

Alcohol Consumption by Genotype and Cirrhosis Status - CP - <country>	tac_<c>_gc_cp	Core population
Alcohol Consumption by Genotype and Cirrhosis Status - TP - <country>	tac_<c>_gc_tp	Target population
Alcohol Consumption by Treatment Regimen and Cirrhosis Status - SP - <country>	tac_<c>_tc_sp	Safety population
CD4 and HIV RNA in Patients with HIV at Baseline by Genotype and Cirrhosis Status - CP - <country>	tlchb_<c>_gc_cp_hiv	Core population: patients with HIV
CD4 and HIV RNA in Patients with HIV at Baseline by Genotype and Cirrhosis Status - TP - <country>	tlchb_<c>_gc_tp_hiv	Target population: patients with HIV
CD4 and HIV RNA in Patients with HIV at Baseline by Treatment Regimen and Cirrhosis Status - SP - <country>	tlchb_<c>_tc_sp_hiv	Safety population: patients with HIV

The layouts of the tables mentioned above are provided in Part II of the SAP (Table Shells).

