    - Depression (No [reference], Yes)
    - Diabetes mellitus (No [reference], Type 1/Type 2)

- Hypertension (No [reference], Yes)
- Immunologically mediated disease (No [reference], Yes)
- Hypothyroidism (No [reference], Yes)
- Alcohol use (None [reference], Yes –occasional, Yes –regular, Exdrinker)
- Key clinical chemistry and hematology laboratory variables at baseline
  - ALT ratio (continuous, see 4.2.6.5)
  - AST ratio (continuous, see 4.2.6.5)
  - Platelets [ $10^9/L$ ] (continuous)
- Prior treatment status (HCV treatment naïve [reference], HCV treatment experienced)

Additionally, an interaction term for cirrhosis status and genotype will be considered. If the most recent stage of liver fibrosis status (No cirrhosis/Transition to cirrhosis vs Cirrhosis), the genotype (G4, G1b vs G1a) or the interaction of both remains in the final model, then additional MLR might be considered for the subgroups concerned, taking into account the treatment regimen (e.g. in cirrhotic G1 patients: RBV vs no RBV and 12 wks vs 24 weeks).

The categories pre-specified above could be modified in the analyses if this is supported by the data (e.g. categories could be combined, if their impact on SVR12 is similar). Furthermore, continuous variables can be replaced by categorical variables.

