**Table 10 Criteria for PCS laboratory values**

Laboratory data	Very Low	Very High
Laboratory hematology		
Hemoglobin [g/L]	<80	
Platelets [ $10^9/L$ ]	<50	
Laboratory clinical chemistry		
ALT		>5 x ULN and >= 2 x baseline
AST		>5 x ULN and >= 2 x baseline
Creatinine [ $\mu\text{mol}/\text{L}$ ]		>132.605
Creatinine clearance [ $\text{mL}/\text{min}$ ]***	<50	

\*\*\* estimated by Cockcroft-Gault-Formula (see above)

Additionally, for hemoglobin and creatinine clearance, the number and percentage of subjects with a maximum Common Terminology Criteria for Adverse Events (CTCAE) Grade of 0, 1, 2, 3, or 4 (see definitions in Table 12) at any post-baseline visit (regardless of the baseline value) through the end of treatment (i.e., Final Treatment Value) will be summarized. For the liver function tests (LFTs) of ALT and AST, the number and percentage of subjects in with a maximum CTCAE Grade of 0, 1, 2, 3, or 4 (see definitions in Table 12) at any post-nadir visit through the end of treatment (i.e., Final Treatment Value) will be summarized. Note, for these analyses, the nadir is used for reference (including baseline).

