#### 4.2.9 Interim Analyses

##### 4.2.9.1 First Interim Analysis

The first interim analysis (IA) was performed in May 2016 (data snapshot: 2 May 2016).

Site information and researcher experience were displayed, as well as patient disposition by genotype and cirrhosis status for the EP.

The CP was restricted to patients with planned treatment duration of 12 weeks who started DAA treatment before 1st April 2016. The following tables were created for the CP

- treatment regimen
- socio-demographic characteristics
- CHC disease characteristics
- CHC Related laboratory variables at baseline
- other key laboratory variables at baseline
- CHC treatment history in treatment experienced patients
- Co-morbidities and co-infections
- alcohol consumption
- CD4 and HIV-RNA in patients with HIV at baseline

All tables were structured by genotype and cirrhosis status. Additionally to the tables above the patient-reported outcomes at baseline were displayed by genotype and cirrhosis status for the CP (i.e. FACIT Fatigue Subscale Score (not normed), PAM-13: Total Score, PAM-13: Level, WPAI: Employment Status, WPAI: Absenteeism (%), WPAI: Presenteeism (%), WPAI: Total Work Productivity Impairment (%), WPAI: Total Activity Impairment (%), PRISM: Self-illness-separation [cm])

Furthermore ANOVAs were conducted in addition to descriptive statistics (i.e. mean, median, SD, SE, 95%CI of the mean) to describe the association between disease characteristics and SIS (PRISM) for categorial variables. The following disease characteristics were considered: sex, age (18-65 years, 66-84 years), race / ethnic origin (White/Caucasian, Asian/Oriental), BMI [kg/sqm] (<25, 25-<30, >=30), HCV genotype (G1/G4), HCV RNA [IU/mL] (800,000,>=800,000), mode of HCV infection (drug use [i.v./non i.v.], blood transfusion or transplantation, unknown, other [all other modes]), years since diagnosis of HCV infection (<=5, 6-10.11-15,>=16), cirrhosis status at BL (yes/no), HCV Co-infection, liver and/or CHC related co-morbidities, other co-morbidities. (For co-morbidities categories the following definition was used: Patients not selecting at least one of the subcategories of the respective category were considered as not having this co-morbidity category.)

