### 5 Data Quality Assurance

Data for this study will be recorded in English by each participating center via an electronic data capture (EDC) system using a web-based eCRF.

A comprehensive data validation program utilizing front-end checks in the eCRF will validate the data. Automated checks for data consistency will be implemented.

Discrepancies need to be solved by the researcher in the eCRF before the module can be completed.

Follow-up on eCRF data for medical plausibility will be done by ABBVIE personnel (or their representatives). Queries will be generated in the eCRF for online resolution at the site. The investigator or an authorized member of the investigator's staff will make any necessary data corrections to the eCRF. All change information, including the date and person performing the corrections, will be available via the audit trail, which is part of the EDC system. The principal investigator of each site will finally review the eCRFs for completeness and accuracy of available data and provide his or her electronic signature and date to the eCRFs as evidence thereof.

All statistical programs employed in the analysis and reporting of the data will be validated according the standard operating procedures of IST and results will be checked for plausibility.

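### The SAP's APRI and FIB-4 formulas give platelets in 10^12/L although its platelet variable is in 10^9/L; taken literally, both indices come out 1,000 times too large on that scale.

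*SAP*

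**What the plan says.** SAP 4.2.6.5 is the only place in either document with a formula for the two indices. Both formulas contain the term "Platelets [10}^{12}/\text{L". For APRI the platelet term reads "Platelets [10}^{12}/\text{L]})$ (APRI= aspartate aminotransferase to platelet ratio index [1", and for FIB-4 it reads "Platelets [10}^{12}/\text{L]} \times \text{Square root of ALT [IU/L". Cleared of extraction marks:

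- APRI = 100 x AST / (ULN of AST x platelets [10^12/L])
- FIB-4 = (age x AST) / (platelets [10^12/L] x square root of ALT)

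The SAP states a platelet unit in two other places. The SVR12 exploratory regression lists "Platelets [ $10^9/L$ ] (continuous") as a covariate, and Table 10 (PCS criteria) has "Platelets [ $10^9/L"] with a low limit of <50. Both are in 10^9/L.

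Protocol sections 9.4.1.1 to 9.4.1.3 say that APRI and FIB-4 will be calculated. A footnote lists the inputs of FIB-4. No formula and no platelet unit is given there.

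The indices are reported in the baseline tables listed in SAP Table 7, for example "CHC Related Laboratory Variables at Baseline by Genotype and Cirrhosis Status - CP", with counterparts for the target and safety populations.

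**The concern.** One laboratory quantity carries two units within the same SAP, three orders of magnitude apart, and the odd one out sits in an operative formula. The multiplier of 100 in APRI is the only constant in either formula, and nothing offsets the change of unit.

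A programmer or validator who follows 4.2.6.5 to the letter would convert the platelet variable to 10^12/L and obtain indices on the wrong scale. One who does not convert has departed from the written specification. In both cases the text and the intended derivation disagree, and the SAP offers no second statement of the formulas to settle it.

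At stake are the APRI and FIB-4 rows that describe liver disease severity at baseline, in a study that presents its results by cirrhosis status. The table family "CHC Related laboratory variables at baseline" is listed for the core population at the first interim analysis and again at the second to fifth (SAP 4.2.9.1 to 4.2.9.5). The SAP describes the fifth as still to be performed.

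**Working it through.** The documents give no numerical APRI or FIB-4 value, so there is no figure of the plan to reproduce. The check is on the formulas themselves.

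**General result.** Let P be the count in 10^9/L. In 10^12/L the same count is P/1,000. Platelets enter each denominator to the first power, so

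- index as written / index with the SAP's platelet variable = P / (P/1,000) = 1,000,

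whatever the age, AST, ALT or ULN.

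**Example using the SAP's own platelet limit.** Table 10 sets the PCS limit at 50 x 10^9/L = 0.050 x 10^12/L. Take AST equal to its ULN, so that AST/ULN = 1:

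- platelets in 10^9/L: APRI = 100 x 1 / 50 = 2.0
- platelets in 10^12/L: APRI = 100 x 1 / 0.050 = 2,000

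**Assumed patient.** Age 55, AST 60 IU/L, ULN of AST 40 IU/L, ALT 64 IU/L (square root 8). These values are assumptions for illustration. At 150 x 10^9/L:

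- APRI = 100 x 60 / (40 x 150) = 1.0; as written, 100 x 60 / (40 x 0.150) = 1,000
- FIB-4 = 55 x 60 / (150 x 8) = 2.75; as written, 55 x 60 / (0.150 x 8) = 2,750

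| Platelets (10^9/L) | APRI, 10^9/L | APRI, as written | FIB-4, 10^9/L | FIB-4, as written |
|---|---|---|---|---|
| 50 | 3.0 | 3,000 | 8.25 | 8,250 |
| 150 | 1.0 | 1,000 | 2.75 | 2,750 |
| 300 | 0.5 | 500 | 1.375 | 1,375 |

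**Range.** Three assumed patients (age/AST/ALT/ULN of 55/60/64/40, 40/30/25/35 and 70/120/100/50) were each evaluated at 50, 100, 150, 200 and 300 x 10^9/L. The ratio was 1,000 in all 15 cases for both indices. With 10^9/L, APRI ran from 0.286 to 4.8 and FIB-4 from 0.8 to 16.8. As written, APRI ran from 285.7 to 4,800 and FIB-4 from 800 to 16,800.

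**Where the indices go.** They are named in the baseline laboratory summary of SAP 4.2.6.5. They are not named in the cirrhosis classification (4.2.1, 4.2.6.2), the core population exclusions (4.2.1), the SVR12 definition (4.1.1), the regression covariate list, the PCS criteria (Table 10) or the CTCAE grades (Table 11).

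**The case against.** The best case against is that this is a slip in a unit label with little practical effect. The 1,000-fold result arises only if someone actively converts platelets to 10^12/L; inserting the 10^9/L variable as it stands gives the usable values. Each formula carries a literature reference, so the programmer did not depend on the printed unit. Programs are to be validated, and "results will be checked for plausibility" (SAP section 5); a baseline APRI near 1,000 would be hard to overlook. The table shells in Part II of the SAP were not available and may state units.

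It can also be said that a formula may prescribe its own input unit, and that neither document gives a cut-off or expected range for the indices that would show which scale is meant.

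Much of this stands as a limit on consequence. No document shows that any output is wrong, and a wrong scale may well have been noticed. It does not repair the text. A formula with its own input unit would be acceptable if the constant matched or a conversion were stated; neither is the case. A misreading of the PDF cannot be excluded without the original, but the same exponent appears in two separate formulas while 10^9 was read correctly elsewhere, which makes it unlikely.

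**Conclusion.** The point holds. The platelet unit in both formulas conflicts with the unit the SAP uses for platelets elsewhere, and literal application inflates APRI and FIB-4 exactly 1,000-fold relative to that variable. The factor rests on no patient assumptions; only the illustrative index values do. Taking 10^9/L as the intended unit rests on the SAP's own usage in the regression list and Table 10.

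The effect is confined to descriptive rows: APRI and FIB-4 in the baseline laboratory tables for the core, target and safety populations, and the corresponding interim tables. The protocol also has both indices calculated during and after treatment, and any such derivation would rely on the same formulas. The primary result and all regression analyses are untouched. Whether any table already produced is affected cannot be told from the documents. The correction should be made, but it is no threat to the study's main conclusions.

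**What to change.** In SAP 4.2.6.5, replace 10^12/L by 10^9/L in the APRI and the FIB-4 formula, so that they match the regression covariate list and Table 10. Confirm which unit the derivation programs used. Check the APRI and FIB-4 rows in the baseline laboratory tables already produced at the interim analyses, and reissue any that are on the wrong scale.

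The cost is two exponents in the text, one program check and a look at existing tables. No new data are needed and no other analysis changes.
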